#### 12.5. Reporting of Adverse Events

Please refer to below for a list of the minimum AE reporting requirements for Investigators. If local regulations or EC require faster reporting, then the Investigator will adhere to those requirements. Reporting of all safety events to the Sponsor will be completed through Investigator submission of the AE eCRF in the remote data capture system.

Events will be reviewed by the Sponsor to determine any reporting obligations to the CA. Reporting will occur within the timelines per local regulations and requirements. The Principal Investigator is responsible to report the events to the EC.

Event's relatedness to the study device and procedure will be assessed according to the following levels of causality:

**Causal relationship-** the serious adverse event is associated with the investigational device, comparator or with procedures beyond reasonable doubt when:

- the event is a known side effect of the product category the device belongs to or of similar devices and procedures;
- the event has a temporal relationship with investigational device use/application or procedures;
- the event involves a body-site or organ that
  - o the investigational device or procedures are applied to;
  - o the investigational device or procedures have an effect on;
- the serious adverse event follows a known response pattern to the medical device (if the response pattern is previously known);
- the discontinuation of medical device application (or reduction of the level of activation/exposure) and reintroduction of its use (or increase of the level of activation/exposure), impact on the serious adverse event (when clinically feasible);
- other possible causes (e.g. an underlying or concurrent illness/ clinical condition or/and an effect of another device, drug or treatment) have been adequately ruled out;
- harm to the subject is due to error in use;
- the event depends on a false result given by the investigational device used for diagnosis, when applicable;

In order to establish the relatedness, not all the criteria listed above might be met at the same time, depending on the type of device/procedures and the serious adverse event.

## MDT20062 SPICE Clinical Investigation Plan Version 4.0 Version Date: 16Jun2022 Page 42 of 75 Medtronic

**Probable-** The relationship with the use of the investigational device or comparator, or the relationship with procedures, seems relevant and/or the event cannot be reasonably explained by another cause.

**Possible-** The relationship with the use of the investigational device or comparator, or the relationship with procedures, is weak but cannot be ruled out completely. Alternative causes are also possible (e.g. an underlying or concurrent illness/ clinical condition or/and an effect of another device, drug or treatment). Cases where relatedness cannot be assessed, or no information has been obtained should also be classified as possible.

**Not related-** Relationship to the device, comparator or procedures can be excluded when:

- the event has no temporal relationship with the use of the investigational device, or the procedures related to application of the investigational device;
- the serious adverse event does not follow a known response pattern to the medical device (if the response pattern is previously known) and is biologically implausible;
- the discontinuation of medical device application or the reduction of the level of activation/exposure when clinically feasible and reintroduction of its use (or increase of the level of activation/exposure), do not impact on the serious adverse event;
- the event involves a body-site or an organ that cannot be affected by the device or procedure;
- the serious adverse event can be attributed to another cause (e.g. an underlying or concurrent illness/ clinical condition, an effect of another device, drug, treatment or other risk factors);
- the event does not depend on a false result given by the investigational device used for diagnosis, when applicable;

In order to establish the non-relatedness, not all the criteria listed above might be met at the same time, depending on the type of device/procedures and the serious adverse event.

Event's Severity will be defined according to the following criteria:

	Event results in mild or transient discomfort, not requiring intervention or treatment; does not limit or interfere with daily activities (e.g., insomnia, mild headache).
IIVIOGETATE	Event is sufficiently discomforting so as to limit or interfere with daily activities; may require interventional treatment (e.g., fever requiring antipyretic medication).
SOVERE	Event results in significant symptoms that prevents normal daily activities may require hospitalization or invasive intervention (e.g., anemia resulting in blood transfusion).

An AE can be classified as severe and not deemed an SAE. Similarly, an SAE is not automatically severe in nature. Severity will be assessed by the Investigator.

Regardless of severity, all AEs occurring during the study must be recorded in the subject's eCRF. The following information and assessments should be documented:

- Type of event (AE term)
- Subject number
- Date of AE onset

 Version 4.0
 Version Date: 16Jun2022
 Page 43 of 75
 Medtronic

- Date of resolution
- Seriousness
- Severity degree: mild / moderate / severe
- Relationship to study device and procedure: causal relationship/ probable/ possible/ not related
- Measures taken
- Outcome of event:
  - not recovered/ not resolved
  - recovered/resolved
  - recovered/ resolved with sequelae
  - recovering/ resolving
  - unknown
  - fatal

The sponsor shall immediately conduct an evaluation of any unanticipated events if determined that the events presents an unreasonable risk to subjects and report the results of such evaluation per the local requirements.

In case of SAEs and SADEs, the following emergency contact may be approached:

## MDT20062 SPICE Clinical Investigation Plan Version 4.0 Version Date: 16Jun2022 Page 44 of 75 Medtronic

#### 12.5.1. Adverse Event and Device Deficiency Classification

All AE and DD will be reviewed by a Sponsor representative. AEs will be classified according to the definitions provided.

Upon receipt of AE at the Sponsor, a representative will review the AE/DD for completeness and accuracy and when necessary will request clarification and/or additional information from the Investigator. The Sponsor will utilize MedDRA, to assign a MedDRA term for each AE based on the information provided by the investigator.

Regulatory reporting of AEs and DDs will be completed according to local regulatory requirements. Refer to

MDT20062 SPICE Clinical Investigation Plan			
Version 4.0	Version Date: 16Jun2022	Page 45 of 75	Medtronic

Table 6 for a list of required investigator and Sponsor reporting requirements and timeframes. It is the responsibility of both investigators and Sponsor, to abide by any additional AE reporting requirements stipulated by the EC responsible for oversight of the study.

For emergency contact regarding SAE and/or SADE, contact a study representative immediately (refer to the study contact list provided in the study site's study documents binder/investigator site file or refer to the Sponsor contact information provided on the title page).

AEs and Deaths will be classified according to the standard definitions as outlined below.

#### **Table 5:Adverse Event Classification Responsibilities**

What is classified?	Who classifies?	Classification Parameters
Relatedness	Investigator	Device, Procedure
Relateuriess	Sponsor	Device, Procedure
Seriousness	Investigator	SAE, DD with SADE potential
Seriousiiess	Sponsor	SAE, DD with SADE potential
	Investigator	Based on presenting signs and symptoms and other supporting data
Diagnosis	Sponsor	MedDRA term assigned based on the data provided by Investigator

#### 12.5.2. Adverse Event and Device Deficiency Reporting Requirements

Regulatory reporting of AEs and DDs will be recorded and reported according to local regulatory requirements. It is the responsibility of the Investigator and the sponsor to abide by the AE reporting requirements stipulated by local law and the study site's EC.

Medtronic

#### **Table 6: Reporting Requirements**

	SAEs
Investigator	shall submit to:
Sponsor	Report to the sponsor, immediately, all serious adverse events and no later than 3 calendar days after investigator first learns of the event.
CA	Submit to CA per local reporting requirement.
EC	Submit to EC per local reporting requirement.
Sponsor shal	I submit to:
CA	Submit to CA per local reporting requirement.
EC	Submit to EC per local reporting requirement.
	ADEs
Investigator	shall submit to:
Sponsor	Submit without unjustified delay, after the investigator first learns of the effect.
CA	Submit to CA per local reporting requirement.
EC	Submit to EC per local reporting requirement.
Sponsor shal	I submit to:
CA	Submit to CA per local reporting requirement.
EC	Submit to EC per local reporting requirement.
	SADEs
Investigator	shall submit to:
Sponsor	Submit immediately after the investigator learns of the event or of new information in relation to an already reported event, and no later than 3 calendar days after the investigator first learns of the effect.
CA	Submit to CA per local reporting requirement
EC	Submit to EC per local reporting requirement.
Sponsor shal	I submit to:
CA	Submit to CA per local reporting requirement.
EC	Submit to EC per local reporting requirement.
Investigators	Submit per local reporting requirement.

Version 4.0 Version Date: 16Jun2022 Page 47 of 75

**Medtronic** 

	All other reportable AEs				
Investigato	shall submit to:				
Sponsor	Submit without unjustified delay after the investigator first learns of the event.				
CA	Submit to CA per local reporting requirement.				
EC	Submit to EC per local reporting requirement.				
	DDs with SADE potential				
Investigator	shall submit to:				
Sponsor	Submit immediately, and no later than 3 calendar days after the investigator first learns of the effect.				
CA	Submit to CA per local reporting requirement.				
EC	Submit to EC per local reporting requirement.				
Sponsor sha	Il submit to:				
CA	Submit to CA per local reporting requirement.				
EC	Submit to EC per local reporting requirement.				
	All other Device Deficiencies				
Investigator	shall submit to:				
Medtronic	Submit without unjustified delay after the investigator first learns of the deficiency.				
CA	Submit to CA per local reporting requirement.				
EC	Submit to EC per local reporting requirement.				

#### 12.6. Subject Death

All subject deaths must be reported by the investigator to Medtronic on an AE form (AE with outcome of fatal) as soon as possible after the investigator first learns of the death. In case of death, there should be one AE with the outcome of fatal.

Local laws and procedures must be followed where applicable. If any system component is returned to the Sponsor, internal return product reporting systems may be used to gather additional information about the returned device/component.

A copy of the death certificate, if available and allowed by state/local law, should be sent to the Sponsor clinical study team. When a death occurs in a hospital, a copy of the death summary report and all relevant hospital records, if available should be sent to the Sponsor clinical study team. If an autopsy is conducted, a copy of the autopsy report should also be sent to the Sponsor clinical study team if available and allowed by state/local law. When the death occurs at a remote study site, it is the investigative study site's responsibility to attempt retrieval of information about the death. Additionally, device disposition information should be updated.

## MDT20062 SPICE Clinical Investigation Plan Version 4.0 Version Date: 16Jun2022 Page 48 of 75 Medtronic

In summary, the following data will be collected:

- Date of death
- Detailed description of death
- Cause of death
- Relatedness to device and procedure
- Device disposition information
- Death summary/hospital records (if available and allowed by state/local law)
- Autopsy report (if available and allowed by state/local law)
- Death certificate (if available and allowed by state/local law)

#### 12.7. Product Complaint Reporting

It is the responsibility of the investigator to report all product complaint(s) associated with a medical device distributed by the Sponsor, regardless whether they are related to intended use, misuse or abuse of the product. Reporting must be done immediately and via the regular channels for market-released products. The reporting of product complaints by the clinical team must be done according to the local Standard Operating Procedures. The Sponsor will notify the RAs (e.g. CA) as applicable for the following incidents immediately upon learning of them and is not limited to AEs and DDs only:

- Any malfunction or deterioration in the characteristics and/or performance of a
  device, as well as any inadequacy in the labeling or instructions for use which led or
  might have led to the death or serious deterioration in the state of health of a patient,
  user, or other person.
- Any technical or medical reason resulting in withdrawal of a device from the market by the manufacturer.
- Any serious deterioration in the state of health, including:
  - Life-threatening illness or injury
  - Permanent impairment of a body function or permanent damage to a body structure
  - A condition necessitating medical or surgical intervention to prevent permanent impairment of a body function or permanent damage to a body structure

#### 13. Statistical Design and Methods

This is a single-center, prospective, non-randomized clinical trial designed to evaluate the technical feasibility (descriptive) of mucosal staining during CCE procedure, using MB-MMX, in CRC high risk population. As a result, no formal sample size was calculated and up to 15 patients are planned to be enrolled to this study. No interim analysis is planned.

## MDT20062 SPICE Clinical Investigation Plan Version 4.0 Version Date: 16Jun2022 Page 49 of 75 Medtronic

As a result, the methods for analysis will be descriptive in nature (frequency and percent as well as distribution measures such as: mean, standard deviation, median and range). 95% confidence intervals will be presented as well.

#### Primary objective:

To demonstrate effective polyp enhancement during a COLON2 Capsule Endoscopy procedure when using MB-MMX as a contrast- enhancement technique.

#### **Primary endpoints:**

- The percent of colonic polyps which have a visible contrast to the healthy colonic mucosa during CCE, as indicated by an experienced reader, using the subjective reader questionnaire (For each polyp was there a contrast between the polyp and the healthy mucosa? Yes/No), out of the examined polyps
- The interference level of detrimental effects on the visualization of the colonic mucosa during CCE, due to use of MB-MMX per colonic segment

Detrimental effect will be considered as any observation, such as an excessive blue dye deposit, dark and dim appearance of the tissue, interfering with tissue visualization and will be evaluated on a scale from 1 (no interference) to 5 (high interference) to evaluate the level of interference, using a subjective reader questionnaire.

#### Secondary objective:

To evaluate the safety of CCE procedure while using MB-MMX.

#### Secondary endpoint:

All AEs will be reported by number, type, relatedness (device/procedure) seriousness, severity and duration. All AEs will be captured, regardless of severity.

This section presents statistical considerations for the study design and provides a high-level description of planned analysis and reporting. More details will be given in a separate Statistical Analysis Plan (SAP) that will be approved before data freeze or lock. Any deviation to the pre-specified statistical analyses will be noted in the study report.

#### 13.1. General Aspects of Analysis

Data analysis will be performed by the sponsor and/or designee.

The analysis will include all of the available information. Demographic and other characteristics will be provided. Summary statistics (arithmetic mean, standard deviation, and range for quantitative variables) will be presented for the total study population. Frequency tables for qualitative data will be provided. All confidence intervals will be presented as 95% confidence intervals unless otherwise stated. For each of the objectives the available data will be summarized, and missing data will be discussed. The main analysis of the study objectives will be based on available data and missing data will not be imputed.

Two analysis sets will be used for the statistical analysis. The definition of each is defined below:

Full Analysis Set (FAS). FAS includes all enrolled subjects:

MDT20062 SPICE Clinical Investigation Plan				
Version 4.0	Version Date: 16Jun2022	Page 50 of 75		Medtronic

- Who signed the informed consent and
- Who satisfied the eligibility criteria
- Ingested the PillCam™ COLON2 capsule

FAS will be used for subject disposition, population and procedures description, for performance and for Safety analyses.

**Per Protocol Analysis Set (PPAS):** PPAS is a subset of the FAS, which includes only subject who have demonstrated all of the following:

- Subjects' compliance to the bowel prep regimen/MB-MMX administration is ≥75% according to each of the following criteria:
  - Total volume of bowel prep material (PEG) consumed is ≥3L (out of 4L in total)
  - Intake of ≥6 MB-MMX tablets (out of total of 8 tablets)
- No major deviations related to Eligibility Criteria and/or Informed Consent
- The capsule reached the colon during the procedure
- Raw data has been generated for the CE procedure

Any deviation from specified statistical plan will be in addition to "per protocol" analysis and will be reported as such. Post-hoc analysis will be conducted according to the existing data gathered, if necessary.

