#### 10.12. Assessment of Safety

AEs information is collected in this study.

To monitor safety in this study, subjects will be asked at each visit about any changes in their medical condition/well-being. All adverse events will be recorded throughout the study, from start of Bowel preparation (1 day prior to the CCE procedure) until the end of the follow up call. AEs should be assessed in terms of their seriousness, type, relatedness (device/procedure), severity and duration. All anticipated adverse events will be collected. Subjects will be able to contact the investigator at any time during the study, if they notice any change in their medical condition/well-being.

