## MDT20062 SPICE Clinical Investigation Plan Version 4.0 Version Date: 16Jun2022 Page 34 of 75 Medtronic

#### 10.15. Subject Exit, Withdrawal or Discontinuation

A study exit eCRF is required for all subjects. The reason for study exit, including screen failure, will be documented on the applicable eCRF and in the subject file. The Sponsor must be informed of each withdrawal case. Prior to exiting a subject from the study, it is recommended to follow the subject until all ongoing device and/or procedure related AEs are resolved or unresolved with no further actions planned. At the completion of the follow-up visit, the subject will be exited from the study. A follow-up eCRF and a Study Exit eCRF will to be completed. Upon exiting from the study, no further study data will be collected, or study visits will occur for the subject, unless the subject has been referred to a colonoscopy procedure post the CCE procedure (de-identified colonoscopy report and images/videos may be collected) and/or AE follow up is required.

Subjects will be informed that they have the right to withdraw from the study at any time, without prejudice to their medical care, and are not obliged to state their reasons.

If the subject wishes to exit from the study (i.e. the subject revokes consent), the study site is required to document the reason for exit on the Exit eCRF. In addition, study site shall follow the regulations set forth by the governing EC. Per ISO14155 guidance, permission may be requested to follow up with the subject outside of the study, due to withdrawal based on issues related to the investigational feature safety or performance.

The investigator may withdraw a subject from the assigned study at any time if any of the following situations arise:

- 1. Subject did not provide consent/ withdrawal of informed consent by the subject
- The Principal Investigator deems that it is in the subject's best interest to withdraw from the study for subject's safety.
- 3. Subject's death
- 4. Occurrence of a Serious Adverse Device Effect (SADE), or severe side effects
- 5. Presence or appearance of any of the exclusion criteria/inclusion criteria not met
- 6. A significant CIP violation, as determined either by the sponsor or the investigator
- 7. Subject noncompliant with study procedures/visits

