#### 12. Adverse Events and Device Deficiencies

#### 12.1. Adverse Events

AEs definitions are provided in Table 3- Adverse Event and Device Deficiency Definitions.

Adverse Events will be collected for all enrolled subjects at the start of the bowel preparation, at day (-1), until the follow-up phone call (visit 3). Medical care will be provided, as defined in the informed consent, for any AE related to study participation, if needed.

Reporting of these events to the Sponsor will occur on an AE Form. Each event must be reported separately. Documented pre-existing conditions are not considered AEs unless the nature or severity of the condition has worsened. Also, Diarrhea<24h after the CCE and mild anal burning/irritation are considered as the expected outcome of the bowel preparation process and shall not be recorded as Adverse Events, as long as the event does not require any medical intervention. Incidental findings observed during CCE video analysis will not be considered as AEs and will not be reported as such. In addition, in case of discovering a pregnancy during the course of the study, it will not be considered as an AE and will not be reported as such.

Per ISO14155:2020, it is required to collect all AEs and DDs. Non-subject AEs are not expected in this study, thus are not collected.

For AEs that require immediate reporting, initial reporting may be done by phone, fax, or on the eCRF completing as much information as possible. The completed AE eCRF must be submitted to the Sponsor as soon as possible.

Any medication/treatment associated with the treatment of an AE must be reported.

Subject deaths are also required to be reported. Refer to Section 12.6 for Subject Death collection and reporting requirements.

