**Table 3- Adverse Event and Device Deficiency Definitions** 

	General
Adverse Event (AE)	Untoward medical occurrence, unintended disease or injury, or untoward clinical signs (including abnormal laboratory findings) in subjects, users or other persons, whether or not related to the investigational medical device and whether anticipated or unanticipated  NOTE 1: This definition includes events related to the investigational medical device or the comparator.  NOTE 2: This definition includes events related to the procedures involved.  NOTE 3: For users or other persons, this definition is restricted to events related to the use of investigational medical devices or comparators.  (ISO 14155:2020, 3.2)
Adverse Device Effect (ADE)	AE related to the use of an investigational medical device  NOTE 1: This definition includes AEs resulting from insufficient or inadequate instructions for use, deployment, implantation, installation, or operation, or any malfunction of the investigational medical device.  NOTE 2: This definition includes any event resulting from use error or from intentional misuse of the investigational medical device.  NOTE 3: this includes 'comparator' if the comparator is a medical device.  (ISO 14155:2020, 3.1)

MDT20062 SPICE Clinical Investigation Plan			
Version 4.0	Version Date: 16Jun2022	Page 40 of 75	Medtronic

Inadequacy of a medical device with respect to its identity, quality, durability, reliability, usability, safety or performance.  NOTE 1: DD include malfunctions, use errors and inadequacy in the information supplied by the manufacturer including labeling.  NOTE2: This definition includes device deficiencies related to the investigational medical device or the comparator. (ISO 14155:2020, 3.19)
Relatedness
An AE that results from the presence or performance of any component of the device.  Device-related: An AE that results from the presence or performance (intended or otherwise) of the device.
An AE that occurs due to any procedure related to the CCE procedure (other than device). The preparation procedure for the CCE procedure in the study includes consumption of bowel preparation materials and MB-MMX tablets (non-MDT products).
Seriousness

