## MDT20062 SPICE Clinical Investigation Plan Version 4.0 Version Date: 16Jun2022 Page 65 of 75 Medtronic

#### Appendix B: Bowel Preparation/MB-MMX administration Deviations

Activity	Deviation specifications					
Diet	Complete deviation if:					
restrictions	• Low-fiber diet was not followed at day 2 and day 3 prior to CCE procedure					
	• Clear liquid diet was not followed 24h prior to and during the CCE procedure					
Bowel prep &	Complete deviation if:					
MB-MMX	• MB-MMX intake is less than 8 tablets. If less than 6 tablets- Exclude from the					
schedule and	analysis					
volume	• MB-MMX is taken after less than 1L of PEG.					
	• MB-MMX timing of intake for 2 nd and 3 rd doses is ±10 min from the allowed					
	intervals (as described in Appendix A)					
	• PEG volume consumed is less than 3.5L.					
	• PEG volume consumed is less than 3L.: Exclude from the analysis.					
	● PEG volume consumed is less than 2.5L: No ingestion					
	• PEG consumed during more than 5h/ less than 2h.					
	• Bowel prep consumed prior to Day (-1)— cancel/postpone the procedure.					
Prucalopride	Complete deviation if Prucalopride tablet was not administrated prior to capsule					
Intake	ingestion.					
Capsule	Complete deviation if the capsule was ingested less than 45m or more than 90m					
ingestion	from Prucalopride intake.					
Boosts	Complete deviation if:					
schedule/	Boost consumption started more than 15m from alert**					
volume	• Complete deviation if less than entire volume was consumed***					

\* In case of a PEG volume deviation s, it should be reported as 1 deviation.

\*\*In case a boost consumption was not started within the regimen timelines and a capsule was excreted within 30 minutes from alert, it will not be considered as a deviation.

\*\*\*In case a capsule is excreted during boost consumption, partial volume of boost consumption will not be considered as a deviation.

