7.1.3 Analysis Sets

Full Analysis Set (FAS) - includes all enrolled subjects who:

- Signed the informed consent and
- Satisfied the eligibility criteria and
- Ingested the PillCam™ COLON2 capsule

Full analysis set (FAS) will include all of the subjects the ingested the capsule and will be used for subject disposition, population and procedures description, for performance and for Safety analyses.

Per Protocol Analysis Set (PPAS) will include a subset of the FAS, which includes only subject who have demonstrated all of the following:

- Subjects' compliance to the bowel prep regimen/MB-MMX administration is ≥75% according to each of the following criteria:
 - Total volume of bowel prep material (PEG) consumed is ≥3L (out of 4L in total)
 - Intake of ≥6 MB-MMX tablets (out of total of 8 tablets)
- No major deviations related to Eligibility Criteria and/or Informed Consent.
- The capsule reached the colon during the procedure.
- Raw data has been generated for the CE procedure.

Any deviation from specified statistical plan will be in addition to "per protocol" analysis and will be reported as such. Post-hoc analysis will be conducted according to the existing data gathered, if necessary.

In addition, as there was an amendment to the CIP, and as a result, the 5 first subjects received a split dose PEG regimen and the rest received a single dose of PEG regimen, a sub-group analysis will be performed as well according to the prep regimen.

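### Safety is analysed only in subjects who swallowed the capsule, although exposure and adverse-event collection begin the day before

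*Protocol*

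**What the plan says.** The plan has two analysis sets, the FAS and the per-protocol set. Protocol 13.1 limits the FAS to enrolled subjects who consented, were eligible and ingested the capsule, and then says "FAS will be used for subject disposition, population and procedures description, for performance and for Safety analyses". SAP 7.1.3 lists the same three conditions and adds: "Full analysis set (FAS) will include all of the subjects the ingested the capsule and will be used for subject disposition", followed by performance and safety. Neither document defines a separate safety set.

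AE collection has a wider base. Protocol 12.1 says "Adverse Events will be collected for all enrolled subjects at the start of the bowel preparation, at day (-1"), and Protocol 10.12 records events "from start of Bowel preparation (1 day prior to the CCE procedure) until the end of the follow up call". Under Protocol 9.2, enrolment needs consent and confirmed eligibility, not ingestion. For relatedness, Protocol Table 3 treats preparation as part of the procedure: "The preparation procedure for the CCE procedure in the study includes consumption of bowel preparation materials and MB-MMX tablets (non-MDT products").

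The AE summary in Protocol 13.4 and SAP 7.9 is the percentage of cases with at least one AE out of the *total cases*, with a 95% CI. Neither document says who the total cases are.

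**The concern.** The secondary objective is the safety of CCE while using MB-MMX. MB-MMX is taken the evening before the capsule. Membership of the safety set is thus conditioned on an event that follows exposure, and an AE can itself prevent that event: Protocol 11.1 lists nausea and vomiting as anticipated effects of the preparation. A subject made too unwell by the preparation to continue is one the safety summary should include, yet the stated set leaves that subject out.

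Two things are at stake: a complete count of subjects with an AE, and a defined denominator for the one AE statistic that has a confidence interval. Protocol 13.5 describes this as the first use of MB-MMX during CCE, and Protocol 6.2 says a larger study may follow favourable results.

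**Working it through.** **No figure to reproduce.** The documents give no AE rate, non-ingestion rate or sample-size calculation. The check sets the definitions side by side and then illustrates the size with assumed counts.

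**1. Can an exposed subject be outside the FAS?**
- Protocol Appendix B: when "PEG volume consumed is less than 2.5L", the instruction is no ingestion.
- Protocol Appendix A (current single-dose schedule): the first 3 MB-MMX tablets (3 × 25 mg = 75 mg) are due at 20:00, after two hourly litres, so after about 2 L by the clock. The stated minimum is 1 L.
- A subject who stops between about 2 L (or 1 L at the minimum) and 2.5 L has therefore taken MB-MMX and is not to ingest. One who stops before the first tablets has PEG exposure only.
- Protocol 10.15: "Subjects will be informed that they have the right to withdraw from the study at any time". Withdrawal after preparation and before ingestion has the same result.
- Complete inability to swallow the capsule (a risk in Protocol 11.1) is a further route. Difficulty followed by ingestion keeps the subject in the FAS.
- Protocol 10.16: subjects are not replaced.

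The Appendix A timing applies only to single-dose subjects. SAP 7.1.3 says "the 5 first subjects received a split dose PEG regimen and the rest received a single dose of PEG regimen", which leaves at most 15 − 5 = 10. No such timing is claimed for the first five.

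**2. Effect on the AE percentage.** Let N be the number exposed, k the non-ingesters, j the non-ingesters with an AE and a the ingesters with an AE.

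- FAS rate = a/(N − k)
- All-exposed rate = (a + j)/N
- All-exposed minus FAS = (k/N) × [j/k − a/(N − k)]

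The FAS count of subjects with an AE is short by j. The FAS percentage is too low only if the non-ingesters' AE rate exceeds the ingesters' rate. Otherwise it is equal or too high.

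Range of the difference for N = 15, letting a run from 0 to N − k (the ends are corner cases):

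| k | j | All-exposed minus FAS (points) |
|---|---|---|
| 1 | 1 | 0 to +6.7 |
| 1 | 0 | −6.7 to 0 |
| 3 | 3 | 0 to +20.0 |
| 3 | 2 | −6.7 to +13.3 |
| 3 | 1 | −13.3 to +6.7 |
| 3 | 0 | −20.0 to 0 |

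Examples with exact (Clopper-Pearson) 95% CIs. The method is an assumption, because the documents name none:

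| Assumed case | FAS | All exposed |
|---|---|---|
| k=1, j=1 | 6/14 = 42.9% (17.7–71.1) | 7/15 = 46.7% (21.3–73.4) |
| k=2, j=2 | 0/13 = 0% (0–24.7) | 2/15 = 13.3% (1.7–40.5) |
| k=2, j=2 | 4/13 = 30.8% (9.1–61.4) | 6/15 = 40.0% (16.3–67.7) |
| k=2, j=0 | 4/13 = 30.8% (9.1–61.4) | 4/15 = 26.7% (7.8–55.1) |
| k=3, j=1 | 7/12 = 58.3% (27.7–84.8) | 8/15 = 53.3% (26.6–78.7) |

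Among at most 10 single-dose subjects with k = 1, the difference is 0 to +10.0 points if the non-ingester had an AE, for example 4/9 = 44.4% (13.7–78.8) against 5/10 = 50.0% (18.7–81.3). If not, it is −(1/10) × (a/9), so −10.0 to 0.

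**The case against.** The best defence is that other text already covers these subjects. Protocol 13.4 says without restriction that all AEs will be reported, Protocol 13.1 says all available information is analysed, and SAP 7.4, whose heading covers dropouts, puts all available data in listings and tabulations. This stands in part: such events may well appear in a listing. But general wording does not displace the explicit assignment of safety to the FAS, and it does not define the denominator. Two analysts could report different numerators and denominators from the same data.

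A second defence is that a *case* can mean a CCE that was performed and read, as Protocol 13.3 uses the word, so that ingesters are the intended population. That reading is possible, but it fits poorly with Table 3, which counts preparation and MB-MMX as procedure, and with AE collection in all enrolled subjects.

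Some points against the reach of the problem are fair. Appendix B's cancel-or-postpone rule is a thin route, because it concerns preparation taken before day -1, and a postponed subject may still ingest. Swallowing disorders are excluded at entry. On the scheduled clock, the PEG window for MB-MMX exposure without ingestion is only 2.0 to 2.5 L. The SAP does not say that the regimen subgroup analysis covers AEs. All counts above are assumed, and the intervals overlap widely. These points limit how often and how much the problem matters. They do not remove the mismatch.

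**Conclusion.** The plan is wrong as written. The only set assigned to safety excludes subjects who were exposed to PEG or MB-MMX and whose AEs the protocol collects. If any such subject has an AE, the FAS count of subjects with an AE is too low. The percentage can err in either direction: by up to 6.7 points with one non-ingester and up to 20.0 with three, assuming 15 exposed. The shift is zero if all ingest. The mismatch follows from the text alone; its size rests on assumed counts. The study is descriptive with no AE threshold, so no prespecified decision changes. It should still be corrected, because safety is the only secondary objective and one subject in 15 is visible in the result.

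A separate drafting point needs settling in the same place. The SAP's FAS bullets require eligibility, while the next sentence takes in everyone who ingested, so the position of an ingester with an eligibility deviation is unclear.

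**What to change.** Before data lock:

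- In SAP 7.1.3, define a Safety Set of all subjects who took any PEG, MB-MMX or later study product, regardless of capsule ingestion or eligibility deviations.
- In SAP 7.9, use that set for all AE summaries and name it as the *total cases* denominator.
- Show PEG-only and MB-MMX-exposed subjects separately, so that PEG-only subjects do not blur the MB-MMX result. With so few subjects, a line listing may be enough for the PEG-only group.
- Keep the FAS for performance, and reconcile its bullets with the sentence that follows them.
- Align Protocol 13.1 at the next amendment.

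The cost is a SAP edit. AEs are already collected from day -1, and Protocol 10.15 has the eCRF completed for withdrawn subjects, including safety information. Protocol Section 13 names the SAP as the place for analysis detail, approved before freeze or lock, so the protocol change can wait. The reported AE rate may come out higher or lower than under the FAS. No clinical rule changes.
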